## Subgroup analysis

We will perform the following subgroup analysis:

- Baseline heavy days (5-11, 12-17, 18-23, 24-30)
- DSM-5 group (mild(2-3), moderate(4-5), severe(>6))
- Geography (Hvidovre, Lyngby, Glostrup, Koege)

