#### Justification of sample size incl. power calculation

The primary outcome measure, i.e. the total number of heavy drinking days, was used for the sample size calculation. Based on data from the study by Johnson et al, where the reduction in the percentage points of the total number of heavy drinking days was 60 pp in the intervention group and 33 pp in the control group. With an alpha of 5%, and a power of 85%, and with an estimated SD of 34.5, the estimated sample size was of 58 patients (29 in each group). With an estimated dropout rate of 60% a total number of 144 patients (72 patients in each arm) was needed (please see below)

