#### Heavy drinking days:

Reduction in heavy drinking days: Topiramate versus placebo: 60.34 contra 32.73

SD estimate 34.5

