# Statistical Principles

# Confidence and P-values

The level of statistical significance will be with an alpha set at 0.05, two-sided testing, and a confidence interval of 95%. There will be no adjustment for multiplicity.

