#### Eligibility

Individuals aged 18-70 diagnosed with AUD according to ICD 10 and DSM-5 with an AUDIT score >15 and with at least 5 heavy drinking days in the past 30 days. Furthermore, no severe psychiatric-, neurological- or somatic disease, history of alcohol withdrawal seizures, diabetes, other substance use disorder, or concomitant pharmacotherapy against alcohol use disorder.

Besides the patients described above, 25 healthy controls matched with sex, age, and education and with no record of AUD were recruited to perform the same fMRI-scans as the patients included in the study.

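### The DSM-5 severity bands as written give a patient with exactly 6 criteria no group, and the 11 subgroup levels come with no treatment-by-subgroup test

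*SAP*

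**What the plan says.** The SAP's Subgroup analysis section is a list of three factors:

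- "Baseline heavy days (5-11, 12-17, 18-23, 24-30" (4 levels)
- "DSM-5 group (mild(2-3), moderate(4-5), severe(>6" (3 levels)
- "Geography (Hvidovre, Lyngby, Glostrup, Koege" (4 levels)

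It states no outcome, model, interaction test or reporting rule, and does not label the results exploratory. The Baseline Patient characteristics section repeats the DSM-5 bands unchanged.

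Other sections bear on the point:

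- **Eligibility** admits "Individuals aged 18-70 diagnosed with AUD according to ICD 10 and DSM-5" and gives no DSM-5 criterion count that would exclude 6.
- **Analysis methods** provides ANOVA for continuous outcomes and chi-square for categorical ones, and mentions no interaction term.
- **Confidence and P-values** states "The level of statistical significance will be with an alpha set at 0.05, two-sided testing" and then "There will be no adjustment for multiplicity".
- **Analysis populations** and **Missing data** set an intention-to-treat analysis of randomised patients with at least one dose, with multiple imputation.
- **Randomization** uses the same four heavy-day bands as strata.

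**The concern.** There are two separate weaknesses in one short section.

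First, the severity bands do not join up. The counts 2-3 and 4-5 are followed by a band that, as printed, begins at 7. A programmer who codes the rule as written gives patients with 6 criteria a missing severity group, and they then fall out of both the baseline summary and the subgroup analysis.

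Second, the section says which subgroups will be examined but not how. A claim that the treatment effect differs between subgroups needs a direct test of that difference. If the general rule (ANOVA at an unadjusted 0.05) is simply applied inside each level, a significant result in one level beside a non-significant one in another can be taken for a differential effect when the effect is the same everywhere. The SAP is the document that should settle this. Its Timing of final analysis section has it signed and uploaded before participants are divided into groups A and B, so the rule should be unambiguous by then.

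**Working it through.** **1. Do the bands cover every eligible patient?**

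| DSM-5 criteria met | Band as printed |
|---|---|
| 2-3 | mild |
| 4-5 | moderate |
| 6 | none |
| 7 or more | severe |

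The gap is the same in both sections. Eligibility does not exclude a count of 6. The SAP does not say how many patients have exactly 6 criteria, so the loss cannot be sized.

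**2. How many levels?** 4 + 3 + 4 = 11.

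**3. False-positive chance if each level is tested separately at 0.05.** This is an assumption, because the SAP does not state the method.

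- If the tests were independent: 1 − 0.95^11 = 1 − 0.569 = 0.431, or 43%.
- Expected false positives per outcome: 11 × 0.05 = 0.55.
- The three factors divide the same patients in three ways, so the tests are not independent. A null simulation (3000 runs per sample size, normal outcome, 1:1 arms, three unrelated equal-sized partitions) gave:

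| Patients | At least one of 11 level tests | At least one of 3 interaction tests |
|---|---|---|
| 46 | 39.6% | 14.7% |
| 58 | 39.1% | 14.3% |
| 114 | 40.4% | 14.4% |
| 144 | 37.7% | 13.9% |

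The range for separate level tests is therefore about 38 to 43%, with little dependence on sample size.

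**4. One interaction test per factor.** If independent: 1 − 0.95^3 = 0.143, or about 14%. The simulation agrees.

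**5. What could a single level show?** Inputs from the sample size section are "Topiramate versus placebo: 60.34 contra 32.73", a difference of 60.34 − 32.73 = 27.61 pp, and "with an estimated SD of 34.5".

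The plan's own figures reproduce: the exact two-sample t-test gives power 0.8496 at 29 per group (stated 0.85) and 0.902 at 34 per group (stated 0.902).

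The SAP does not give the number randomised or the sizes of the levels. The table below assumes equal-sized levels and gives power for the full 27.61 pp, with per-arm numbers rounded down:

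| Patients with week-26 data | Per arm, 4-level factor | Power | Per arm, 3-level factor | Power |
|---|---|---|---|---|
| 46 (114 × 0.4) | 5.75 → 5 | 20% | 7.67 → 7 | 28% |
| 58 (planned evaluable) | 7.25 → 7 | 28% | 9.67 → 9 | 36% |
| 144 (all planned, as if fully observed) | 18 | 65% | 24 | 78% |

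At 7 per arm, the difference detectable with 85% power is about 60 pp by the exact t-test. The normal approximation gives (1.96 + 1.036) × 34.5 × √(2/7) ≈ 55 pp. Even in the most favourable row, a mixture of significant and non-significant levels would be expected when the effect is the same in all of them. Within-level p-values therefore cannot answer the subgroup question.

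**The case against.** The strongest reply on the bands is that the printed sign is loose notation or a symbol lost from the PDF. The SAP itself supports this: Eligibility asks for an AUDIT score above 15, yet the baseline table has an AUDIT band of 15-19, which starts at the value the sign would exclude. The three severity labels are evidently meant to cover everyone. This is a fair argument about intent, and a reader should not infer that the plan means to exclude patients with 6 criteria. It does not remove the need to correct a rule that fails when coded as printed in two places.

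On testing, the reply is that the SAP never says it will run 11 within-level tests, that an ANOVA could carry an interaction term, and that the subgroups stand apart from the listed endpoints. This also stands in part. The 38 to 43% describes one way of filling a gap in the plan and is not a property of the plan. The gap itself remains.

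A reader might also infer that the subgroups are formed from the few patients who complete. The documents do not support that: the analysis is ITT with multiple imputation, so all treated patients enter. Observed week-26 data would still come mainly from those who stayed, with dropout reported as nearly 60%, and imputation adds no observed outcomes.

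Finally, one might want baseline heavy days as a continuous term in place of the bands. That would assume a particular shape of interaction and set aside the randomisation strata. It is a trade-off and not a correction.

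**Conclusion.** The point holds as a minor one. The DSM-5 bands leave a count of exactly 6 unassigned in the baseline table and in the subgroup rule. The number of patients affected is unknown, and the cause may be a slip of notation. The subgroup section lists 11 levels without stating how a difference in treatment effect would be tested, under a plan that makes no multiplicity adjustment.

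If the levels were tested one by one at 0.05, the chance of at least one false positive per outcome would be about 38% (simulated, overlapping partitions) to 43% (independent tests). One interaction test per factor brings it to about 14%, which is lower but still above 5%. These figures assume no effect in any level, and the simulation also assumes equal-sized levels and unrelated factors. The primary analysis does not use the subgroups and is unaffected.

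**What to change.** 1. In Baseline Patient characteristics and in Subgroup analysis, write the top DSM-5 band as severe (6 or more).
2. In Subgroup analysis, name the outcome as the primary endpoint and add that each of the three factors is tested by one treatment-by-subgroup interaction in the primary outcome model on the ITT set, with the missing-data handling already planned. Keep the four heavy-day bands, since they are the randomisation strata.
3. State that level-specific estimates are given with 95% confidence intervals, labelled exploratory, without within-level p-values.

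The cost is a small correction in two places and a few added sentences. No new data are needed. The within-level p-values are given up. Three interaction tests still carry about a 14% chance of a false positive, which is the reason for the exploratory label.

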#### Posthoc analysis

- SPECT-scan: The difference in baseline SBR (Striatum, Putamen, Caudatus) with a healthy control sample.
- Data from the 6 months follow-up (PACS, PEth, AUDIT, Fagerstroems for nicotine)
- Plasma exanetide concentration level and antibody-level related to heavy drinking days
- Plasma FGF-21 levels
- Urine oxidative stress parameters
- Plasma bone markers (TRAP-5b, CTX, PINP)
- **Proteomic fingerprint**
- fMRI Spatial working memory (N-back task)

# Missing data

Missing data will be imputed using the multiple imputation method. However, for multiple imputations to work properly we need to assume that the data are missing at random (MAR) which may not be the case in our study. Consequently, as a sensitivity analysis of handling the missing data, we will consider two realistic alternatives for the missing mechanism: 1) to assume that all non-observed individuals at 26 weeks have reverted to their pre-study drinking habit, and 2) that all non-observed individuals at 26 weeks have halved

**EXALT** study

Statistical Analysis Plan

Edition: 1.0

EudraCT 2016-003343-11

their drinking. If only multiple outcomes are missing then we will use a linear mixed-effect model which is an extension of the ANOVA model for analyzing the data.

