# Study Methods

#### Trial design

The EXALT trial¹ was a randomised, double-blinded, place bo-controlled clinical trial for 26 weeks and a long term follow up 26 weeks after the end of participation in the main trial. Comparative treatment regimens were once-weekly injections with exenatide 2 mg (Bydureon®) or placebo (saline) as a supplement to cognitive behavioral therapy. Baseline data were collected at the screening session. Follow-up meetings were scheduled at weeks 4, 12, 20, and a final evaluation at week 26.

A subgroup of patients had a baseline SPECT- and an fMRI scan or just an fMRI scan performed before receiving 1. injection, and again when they finalized the study.

A group of 25 individuals matched with age, gender, education, and no history of alcohol use disorder had the same screening blood-samples and the same fMRI scan performed.

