## Sample size

The original sample size calculation was performed with an estimated drop-out rate of 40 % and a power of 90%. That led to a total number of 114 patients to include. Please see appendix 1. In May 2019 when recruitment was almost finished, the dropout rate was nearly 60%. We choose as a consequence to do a

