# Analysis

#### Outcome definitions

#### Primary endpoint

Percentage of heavy drinking days during the last 30 days, at follow-up after 26 weeks of treatment adjusted for baseline (percentage points (pp)). A heavy-drinking day is defined as a day with an excess intake of 60/48 grams (men/women) of alcohol per day. Data will be registered via the Timeline-Follow-Back-method (TLFB).

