### Analysis methods

All continuous outcomes, i.e., change in metabolic parameters, weight, body composition parameters, alcohol use, etc. will be analyzed using ANOVA from baseline to last observation endpoint. Categorical outcomes will be analyzed using chi-square analyses. As the study was conducted as a randomized trial, no covariates adjustment is in principle necessary to assess causal effects.

Edition: 1.0

26.05.20

Statistical Analysis Plan

EudraCT 2016-003343-11

We will use residual plots and qq-plots in combination with Wally plots to validate the normality assumptions of the residuals in the ANOVA models. If the distributional assumption about normality of the residuals does not hold then we will first see if a log-transform of the outcome will result in a model fit that does not appear to violate the assumptions of normality. If the log-transform still does not hold, our next step will be to consider if the lack of fit is caused by inflation, e.g. due to too many observations being zero. Should that be the case we will replace the standard ANOVA model with a zero-inflated gaussian mixture model for the analyses. Should none of these approaches work we will use quantile regression and model the median outcome instead.

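### The SAP gives overlapping rules, with no order of precedence, for missing week-26 heavy drinking days, and does not say whether the week 4, 12 and 20 data are used

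*SAP*

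**What the plan says.** The SAP's Primary endpoint section defines the outcome at one time: "Percentage of heavy drinking days during the last 30 days, at follow-up after 26 weeks of treatment adjusted for baseline". Three statements then bear on how a missing value of it is handled.

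- Missing data, opening: "Missing data will be imputed using the multiple imputation method". No condition is attached. The section doubts the missing-at-random (MAR) assumption and sets two fixed scenarios against it as sensitivity analyses: return to pre-study drinking, and drinking halved.
- Missing data, close: "If only multiple outcomes are missing then we will use a linear mixed-effect model which is an extension of the ANOVA model".
- Analysis methods: continuous outcomes "will be analyzed using ANOVA from baseline to last observation endpoint". Fallbacks for non-normal residuals follow: a log-transform, a zero-inflated model, then median regression.

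On visits, Trial design says: "Follow-up meetings were scheduled at weeks 4, 12, 20, and a final evaluation at week 26". On loss, Sample size says that in May 2019 "the dropout rate was nearly 60" per cent. Withdrawal/Follow up adds that patients who left after at least eight weeks were encouraged to have the final assessment when they withdrew.

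The SAP gives no imputation variables, no number of imputations, and no mixed-model terms or covariance. It does not say whether the interim visits enter either method.

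**The concern.** With this much loss, the handling of missing week-26 values largely determines the primary result. Two rules claim the same values, neither has precedence, and a third section describes a different analysis. The test is at a fixed level ("The level of statistical significance will be with an alpha set at 0.05, two-sided testing"), but the estimate being tested is not fixed.

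The analysis is to be done under A/B labels. Those labels hide which arm is exenatide, but they do not hide which method gives the larger difference. If the choice stays open, it can be made after the A-versus-B results are seen.

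**Working it through.** **1. Can an ordinary drop-out meet the mixed-model trigger?** The wording allows three readings.

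- Several outcome variables are missing. A patient with no final assessment lacks heavy drinking days, PEth, craving score and others, so the trigger is met.
- Several visits are missing. A patient who left before week 20 lacks weeks 20 and 26, so the trigger is met. A patient who missed only week 26 would not meet it.
- Outcomes but no covariates are missing. Baseline heavy drinking days should be complete, because entry requires AUD "with at least 5 heavy drinking days in the past 30 days" and randomisation is stratified on them. Any missing week-26 value then meets the trigger.

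So a drop-out can meet each reading, and the unconditional imputation rule covers the same value.

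**2. The plan's own figures.** Difference: 60.34 − 32.73 = 27.61 pp; SD 34.5. Exact two-sample t-test power is 0.850 at 29 per group and 0.902 at 34, as stated. Drop-out inflation: 68/(1 − 0.40) = 113.3, so 114 as stated; 58/(1 − 0.60) = 145 against 144 stated, which is immaterial. Planning standard error: 34.5 × √(2/29) = 9.1 pp.

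**3. How many values are at issue.** The final number randomised is not given, so the SAP's planning totals of 114 and 144 serve as an assumed range. At 60% loss, 0.6 × 114 = 68 to 0.6 × 144 = 86 values are missing, and 46 to 58 are observed. This assumes that no drop-out has a usable final value.

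**4. Simulation with no true effect.** Assumed: baseline plus four visits, SD 34.5, AR(1) correlation 0.6 or 0.8, 57 or 72 per arm, 60% to 63% monotone loss, 1,000 trials per setting. Missing week-26 values were completed by arm from baseline only, or from baseline plus weeks 4, 12 and 20. Both estimates were then adjusted for baseline. Ranges over the four combinations of size and correlation:

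| Drop-out log-odds per SD of drinking (arm 0 / arm 1) | Mean, baseline only (pp) | Mean, all visits (pp) | SD of same-trial difference (pp) | Trials differing by more than 5 pp |
|---|---|---|---|---|
| 0 / 0 | −0.1 to 0.3 | −0.1 to 0.4 | 3.5 to 4.8 | 15% to 28% |
| 0.8 / 0.8 | −0.4 to 0.5 | −0.3 to 0.1 | 5.4 to 7.0 | 35% to 43% |
| 0.3 / 1.0 | −5.4 to −4.8 | −0.3 to −0.1 | 5.1 to 6.7 | 46% to 52% |

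Variance ratios (all visits to baseline only) under random drop-out:

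- 57 per arm: (9.8/10.3)² = 0.91 and (8.9/9.7)² = 0.84
- 72 per arm: (9.0/9.3)² = 0.94 and (7.9/8.7)² = 0.82

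That is 6% to 18% less variance. The gain is not assured when drop-out follows drinking: with 57 per arm, correlation 0.6 and slopes 0.3/1.0, the SDs are 10.9 (baseline only) and 11.8 (all visits).

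**5. Simulation at the planned effect.** Assumed: 72 per arm, true difference 27.61 pp, 60% loss, baseline in both analyses, correlation 0.5 to 0.85, drop-out slope 0.5 to 1.0 per SD in both arms.

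- Week-26-only bias is about 0.3 to 2.4 pp. With all visits it is at most about 0.3 pp.
- A second set with the same main assumptions gave a week-26-only bias of 0.9 to 3.9 pp under AR(1) and 0.3 to 2.2 pp under exchangeable correlation.
- Under random drop-out, all visits give about 5% to 20% less variance.
- The two estimates from one trial differ with an SD of 2 to 4 pp.

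Over both simulations, the same-trial SD of 2 to 7.0 pp is 2/9.1 = 0.2 to 7.0/9.1 = 0.8 planning standard errors.

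**The case against.** A reader might infer that the SAP sets two primary methods, or that multiple imputation is never used for the primary endpoint. The text supports neither. Imputation is unconditional, the mixed model is conditional, and neither is labelled primary. The second inference also needs the word *multiple* dropped from the trigger. What stands is an undefined trigger and no precedence.

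Nor should the simulated gap be read as imputation against mixed model. Under MAR, the two on the same variables nearly agree. The gap comes from using or omitting the interim visits, and the SAP assigns those visits to neither method.

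Further limits are fair:

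- Drop-out is not the same as a missing final value. Some patients who withdrew may have had an early final assessment.
- The SAP lists the interim visits under the timing of outcome assessments but does not say that Timeline-Follow-Back data were taken at each.
- The ANOVA sentence may mean the last available value. That would not discard drop-outs' data, but it would not be a week-26 analysis either.
- The link between drop-out and relapse is a sensitivity assumption, and the SAP already plans scenarios for it.
- Making drop-out depend on the last observed value favours the all-visit analysis by construction.

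These points reduce the size of the problem. They do not settle which rule applies.

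**Conclusion.** The concern holds as a conflict of rules on the primary endpoint: two overlapping instructions without precedence, and a third that does not match week 26. Its effect is moderate. Under the stated assumptions, leaving out the interim visits biases the estimate by about 0.3 to 2.4 pp. The bias reaches about 4 pp in other settings, and about 5 pp if drop-out depends on drinking more strongly in one arm. The choice can also move a single trial's estimate by a fraction of a standard error in either direction, which could change a borderline conclusion. Against a planned 27.61 pp it would not by itself create or erase an effect of that size.

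The sizes rest on assumed correlations and drop-out models, on about 60% of week-26 values being missing, and on interim drinking data existing. The conflict in the text rests on none of these.

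**What to change.** Before participants are divided into groups A and B, name one primary method for percent heavy drinking days at week 26. It should cover all analysed patients, adjust for baseline heavy drinking days, and use the week 4, 12 and 20 Timeline-Follow-Back values if they were recorded. Either choice is sound:

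- **Multiple imputation by arm**, with those values and the stratification factors in the imputation model and the number of imputations stated. This keeps the section's leading method and the fallbacks for non-normality.
- **A linear mixed model** with arm, visit, arm-by-visit, baseline and baseline-by-visit terms and unstructured covariance, with the week-26 arm difference as the primary contrast. The SAP would then need to say what replaces the ANOVA fallbacks.

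Make the other method supportive. Delete the undefined trigger from Missing data. In Analysis methods, replace the reference to the last observation with week 26. State how a final assessment made early, at withdrawal, enters the week-26 analysis.

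The cost is SAP wording and slightly more programming, with no new data collection.

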## Additional analysis

Our primary analysis compares treated with untreated in an intention-to-treat (ITT) setup which provides valid estimates of the real-world effects. To get an estimate of the complier-average causal effect we will use information from the questionnaire of the drop-outs using the principal stratification approach of Frangakis and Robin

#### Harms

Safety data has been collected in the 26 weeks of inclusion and up until 10 weeks after termination of the study for all individuals. Data has been classified as Serious Adverse Events (SAE), Adverse Events (AE), and Adverse Reactions (AR). All collected safety data will be summarized in a table with incidence cases.

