# Psychiatric Centre Copenhagen, Rigshospitalet

26.05.20

Statistical Analysis Plan

Edition: 1.0

EudraCT 2016-003343-11

new power calculation with a drop out rate of 60% and a power of 85% (please see below). Due to a lack of patients to be included we stopped recruitment 1st of October 2019.

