#### Adherence and protocol deviations

Adherence to the intervention was defined by no more than 3 missed consecutive injections, or 5 missed injections in total during the 26-week period. The un-blinded project nurses kept an individual injection schedule per patient and thereby kept track of the extent of exposure. Adherence to the intervention will be presented as a table of distribution of percentage of weeks with study medication injections in the main treatment period. Protocol deviations will be presented in a table divided into the categories: study procedure, eligibility, and randomisation. Only protocol deviations regarding "lost to follow up" and "withdrawal" will be summarized in the section named this.

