# Withdrawal/Follow up

All patients who have withdrawn from the intervention and have been included for at least eight weeks (steady-state plasma level) were encouraged to participate in the last week 26 follow-up including brain scans at the time of withdrawal. If successful, individuals will be contacted for a long-term follow-up after further 26 weeks. All other individuals e.g individuals who withdraw before eight weeks and lost to follow-up will not be contacted for a long-term follow-up. Data will be presented in a Kaplan Meyer survival curve

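### The harms table makes no allowance for time at risk although drop-out was nearly 60%; if drop-out differs between arms, crude incidence will tend to understate harm in the arm with more loss

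*SAP*

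**What the plan says.** The Harms section describes collection as follows: "Safety data has been collected in the 26 weeks of inclusion and up until 10 weeks after termination of the study for all individuals". Events are classed as SAE, AE or AR. The summary is then fixed in one sentence: "All collected safety data will be summarized in a table with incidence cases". It does not say whether patients or events are counted, over what denominator, by which arm, or in which period. The section on analysis populations applies to all analyses and takes randomised patients with at least one dose, so a patient denominator can be inferred.

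Three other sections bear on time at risk:

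- **Sample size:** "In May 2019 when recruitment was almost finished, the dropout rate was nearly 60"%. The figure is pooled over arms.
- **Adherence and protocol deviations:** "The un-blinded project nurses kept an individual injection schedule per patient and thereby kept track of the extent of exposure". This record feeds a table of the percentage of weeks with injections and is not linked to harms.
- **Recruitment:** all remaining patients were stopped on 14 March 2020 because of COVID-19, whereas the last main-study visit had been planned for 8 April 2020.

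**The concern.** When most patients stop early, the number of weeks in which an event could occur or be recorded varies widely between patients. A crude count or percentage treats a short and a full period of observation alike. If one arm loses more patients, or loses them sooner, it accrues less time at risk and tends to show fewer events at the same underlying rate.

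Pooling the treatment weeks with the weeks after stopping adds a second problem. The mix of the two differs between early stoppers and completers, and a real difference that exists only during treatment is diluted. Readers will rely on this table to judge the safety of a weekly injected drug in a patient group that is new for it.

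**Working it through.** **Plan's own figure.** The Harms section has none to reproduce. The 60% enters arithmetic only in the sample size: 58/(1 − 0.60) = 145, against the stated 144. There too it is one pooled rate.

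**Inputs from the SAP.** Treatment period 26 weeks; post-termination collection 10 weeks; drop-out about 60% overall.

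**Assumptions.** The SAP gives neither drop-out by arm nor drop-out times, so these are mine: drop-outs leave at week 8, the 10 weeks run from each patient's own stop, and events occur at a constant rate that is equal in both arms. Week 8 is the only withdrawal time the SAP names, and there it is a threshold for inviting withdrawn patients to the final visit, not a typical drop-out time.

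**Observation per patient.** Completer: 26 + 10 = 36 weeks. Drop-out at week 8: 8 + 10 = 18 weeks.

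**Mean observation per arm** = (1 − d) × 36 + d × 18, where d is the arm's drop-out proportion. With equal true rates, the expected ratio of event counts is the ratio of these means.

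| Drop-out, arm A / arm B | Mean weeks A | Mean weeks B | Count ratio B/A |
|---|---|---|---|
| 60% / 60% | 25.2 | 25.2 | 1.00 |
| 55% / 65% | 26.1 | 24.3 | 0.93 |
| 50% / 70% | 27.0 | 23.4 | 0.87 |
| 40% / 80% | 28.8 | 21.6 | 0.75 |

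For 50% / 70%: 0.5 × 36 + 0.5 × 18 = 27.0; 0.3 × 36 + 0.7 × 18 = 23.4; 23.4/27.0 = 0.867, or 13% fewer events. Moving the drop-out week from 4 to 13 changes this ratio from 0.82 to 0.91.

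**Treatment weeks only,** 50% / 70%: 0.5 × 26 + 0.5 × 8 = 17.0; 0.3 × 26 + 0.7 × 8 = 13.4; ratio 0.79, or 21% fewer.

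**Percentage of patients instead of counts.** Take an assumed rate of 0.02 per week. The chance of at least one event is 1 − exp(−0.02 × 36) = 0.513 for a completer and 1 − exp(−0.02 × 18) = 0.302 for a drop-out. Arm A: 0.5 × 0.513 + 0.5 × 0.302 = 0.408. Arm B: 0.3 × 0.513 + 0.7 × 0.302 = 0.366. The ratio is 0.90, so a patient denominator lessens the distortion but does not remove it.

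**Dilution from pooling periods.** Suppose 60% drop-out at week 8 in both arms, and a drug that doubles the event rate during treatment only. Mean treatment time is 0.4 × 26 + 0.6 × 8 = 15.2 of 25.2 weeks. The pooled rate ratio is (15.2 × 2 + 10)/25.2 = 1.60 instead of 2.0. Any drug effect that lingers after the last injection would make this dilution smaller.

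**The case against.** Several points on the other side stand.

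- **A reader might infer that only raw counts will be shown.** The SAP does not say that. *Incidence* can mean the number or share of patients with an event, and the analysis-population section supplies a denominator. A crude share still ignores time at risk, as shown above.
- **A reader might infer that safety follow-up differs two-fold between arms.** The documents do not support this. The ratio 36/18 = 2.0 compares one completer with one patient who stops at exactly week 8, with the 10 weeks counted from that patient's own stop. For a stop at week 4 it is 36/14 = 2.6, and at week 20 it is 36/30 = 1.2. If the Harms wording means that everyone was followed for the full 36 weeks, it is 1.0. Treatment time would still differ: 8 of 36 weeks (22%) against 26 of 36 (72%).
- **A reader might infer that one arm will in fact look safer.** That needs unequal loss, and the SAP reports only a pooled rate as of May 2019. Events that lead to withdrawal are already counted. For events in the first weeks the bias is small, since even a week-1 drop-out has 11 weeks of safety observation on the per-patient reading.
- **Patient-time rates can mislead the other way.** If events cluster early and are equally frequent per patient, dividing by patient-time makes the arm with more loss look worse by 27.0/23.4 = 1.15, or 17.0/13.4 = 1.27 on treatment time. Such rates should therefore supplement the patient percentages.
- **Some context is already planned.** The adherence table and the survival curve under Withdrawal/Follow up will show exposure and retention, though neither is tied to harms. The conduct of safety follow-up after early stopping may be set out in the protocol.

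The COVID-19 stop adds little: 14 March to 8 April is 25 days, and the later date was the last visit planned for anyone.

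**Conclusion.** The point holds in a conditional form. The SAP fixes a pooled incidence table that makes no allowance for time at risk, in a trial with nearly 60% drop-out and with individual exposure on record. If drop-out or its timing differs between arms, crude incidence will tend to understate harm in the arm with more loss. The 13% (21% on treatment time) rests on the assumed week-8 drop-out, the 50% / 70% split and a constant event rate; it is an illustration, not an estimate for this trial. With equal drop-out at the same times this bias is nil, although pooling the two periods can still dilute a difference confined to treatment. The stated method can be improved cheaply. Because the SAP is to be signed before patients are divided into groups A and B, the definitions belong in it.

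**What to change.** Replace the summary sentence under Harms with a rule that, for each treatment group:

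1. reports the number and percentage of dosed patients with at least one SAE, AE and AR, and the number of events;
2. adds events per patient-time as a supplement, using the injection schedules for treatment time;
3. tabulates the treatment and post-treatment periods separately, with the end of the on-treatment period set and justified by the sponsor, consistently with the eight weeks to steady state cited under Withdrawal/Follow up;
4. states from when the 10-week window runs for patients who stop early, or refers to the protocol section that says so.

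The exposure data are already held, so the cost is a little table programming and a larger safety table. Patient-time rates assume a roughly constant event rate, so they must be read beside the patient percentages and not replace them.
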